Acute Effect of Inhibitory Kinesio-tape of the Upper Trapezius on Lower Trapezius Muscle Excitation in Healthy Shoulders

NCT04711447

March 14th, 2023

METHODS

Design

A repeated-measures, crossover design was used to determine the acute effect of KT applied to the UT on muscle excitation of the LT. Participants were asked to perform a repeated arm elevation task during three different taping conditions: no KT, experimental KT and sham KT. During each taping condition, participants performed a bilateral repeated arm elevation task during two loading conditions: no load and loaded with 2.3 kilograms. All six conditions were tested during one visit, with the no load condition preceding the loaded condition for each taping condition. A baseline trial (no KT; N-KT) was performed first, followed by both an experimental-KT (E-KT) and sham-KT (S-KT) condition. The order of the E-KT and S-KT conditions were randomized and counterbalanced (Research Randomizer v4.0, Social Psychology Network, Lancaster, PA, United States) (Figure 1). Testing for each tape condition during both the no load and loaded conditions lasted approximately 10-minutes, requiring a total of 45-minutes of testing time per participant including screening, EMG set-up and clean-up. No wash-out period was given between S-KT and E-KT taping conditions; the first tape condition was removed upon completion of the arm elevation task and the second tape condition was applied immediately after. KT was applied to the UT and muscle excitation (EMG amplitude) was measured in the LT using the same 32-electrode high-density surface electromyography (HD-sEMG) grid during the repeated arm elevation task. All data were collected in a laboratory setting at the University of Manitoba.

Participants

Twenty-two right-handed individuals between the ages of 18 and 60 with no current shoulder pain or pathology participated in the study (24 ± 3 years). Participants were recruited via convenience sampling of the University of Manitoba Faculty of Kinesiology and Recreation Management student and staff population, and the general population in the surrounding community. A potential participant was excluded if they had a recent history (<6 months) of injury or orthopedic disorder of the shoulder, upper back or neck (e.g. rotator cuff tears, disc pathologies, etc.), neurological or musculoskeletal disorder (e.g. epilepsy, multiple sclerosis, etc.), current pain in the shoulder, upper back or neck and previous allergies or skin sensitivity to tape or adhesives. Participants were not screened for scapular dyskinesis. All experimental procedures were approved by the University of Manitoba's Education/ Nursing Research Ethics Board in the spirit of the Helsinki Declaration. Participants received complete written and verbal details of the experimental procedures and potential risks involved prior to providing informed consent. This clinical trial was registered retroactively in the U.S. National Library of Medicine ClinicalTrials.gov database: NCT04711447.

Kinesio-tape (KT)

Each participant completed an arm elevation task under three taping conditions: first with no tape (N-KT), then with experimental-KT (E-KT) and sham-KT (S-KT) in random order (Figure 1). The KT was applied by one of two Certified Athletic Therapists, each with training and over four years of experience with KT. The therapists were the only individuals aware of the taping condition as the researchers and participants were blinded. The skin over the right UT was cleaned with an alcohol swab prior to the placement of the KT. The KT (2" Leukotape K, BSN Medical, Hamburg, Germany) was applied to dry skin

over the UT approximately parallel to its fibers beginning proximally, 5-7.5cm lateral to C3 spinous process, and finishing distally at the right acromion process (Figure 2A). The S-KT was applied with no tension (0% stretch) and the participant was instructed to look straight ahead to maintain a neutral neck and shoulder position (Zanca et al 2016). The E-KT was applied using an inhibitory taping technique previously described for the gastrocnemius (Davison et al. 2016), modified for the UT. Specifically, the UT was placed in a stretched position by instructing the participant to bring their chin to chest and rotate to their left shoulder. The proximal tape anchor was applied lateral to C3 with no tension, stretched to ~125% tension from original length, and laid onto the skin over the right UT. The distal tape anchor was then applied to the UT bony attachment at the acromion with zero tension (Davison et al. 2016). The Certified Athletic Therapists used their clinical judgement to subjectively measure ~125% tension, first by stretching the tape to 200% of its original length, reducing to 150%, and then to ~125%. The participant was then instructed to relax their head back into neutral once the KT was applied.

High-density surface electromyography (HD-sEMG)

Muscle excitation of the LT was measured during the arm elevation task of all three taping conditions using HD-sEMG. Prior to electrode placement, the skin was shaved (if necessary), cleaned with an abrasive paste (Nuprep, Weaver and Company, Aurora, Colorado, USA), and wiped with an isopropyl alcohol swab (70%). One semi-disposable 32-electrode grid (GR10MM08804, OT Biolettronica, Torino, Italy) arranged in eight rows and four columns (gold coated, interelectrode distance, 10mm) was applied to the LT approximately halfway between T12 and the middle of the spine of the right scapula (Figure 2B). Electrode rows were placed approximately parallel to the LT's fiber direction.

The electrode grid was covered with a disposable adhesive foam matrix (KITAD4x8NM6, OT Bioelettronica, Torino, Italy) filled with conductive paste (Ten20, Weaver and Company, Aurora, Colorado, USA) and secured to the participant's skin for the duration of the visit with tape (Hypafix, BSN Medical, Hamburg, Germany). Ground electrodes were placed at the participant's wrist and C7 spinous process (Figure 2B).

Repeated arm elevation task

For each tape and load condition participants performed ten repetitions of standing bilateral arm abduction in the frontal plane beginning with their arm resting by their side (Figure 2C). Participants were instructed to raise their arms bilaterally to full shoulder abduction (180°) while keeping their elbow fully extended and forearm supinated (Figure 2D). Participants were familiarized with performing the arm elevation task immediately prior to performing the N-KT condition (Figure 1). A research assistant performed the arm elevation task at a rate of 40 beats per minute while participants were asked to follow a metronome and mimic the researcher. Each repetition lasted for a total of three beats, or ~3 seconds, beginning with their arms by their sides. The participant's arm ascended into abduction where the first beat occurred at maximal abduction, followed by descending back to starting position where the second beat occurred. The third beat acted as a rest beat before beginning the next repetition and continued this for a total of 10 repetitions. An external load of 2.3kg was utilized to increase muscular demand while still allowing the participant to perform the required volume of arm abductions. Clinically, a load of 2.3kg is used to exacerbate scapular dyskinesia when present (McClure et al 2009).

Data processing and extraction

HD-sEMG was recorded and processed using a Dell laptop (Latitude 5500, Dell Canada, Toronto, ON, Canada). HD-sEMG signals were recorded in monopolar and converted to digital using a 16-bit multichannel amplifier (Quattrocento, 400-channel EMG amplifier, OT Biolettronica, Torino, Italy; Common Mode Rejection Ratio > 95 dB). Signals were amplified (150V/V), sampled at 2048 Hz and bandpass filtered (10–500 Hz; -3 dB bandwidth). Data were further filtered using a 30 Hz highpass filter (2nd order Butterworth) to minimize electrocardiographic noise (Drake and Callaghan 2006). Single differential spatial filtering of adjacent monopolar signals within each row were calculated using OT Biolab + (OT Biolettronica, Torino, Italy), resulting in three differential values for each row of the grid. Root mean square (RMS) was then calculated for each differential signal and averaged within rows to determine individual row RMS (e.g. row 1 RMS). Shifts in the distribution of EMG amplitude within the LT were considered to be indicated by statistically significant differences in row RMS between conditions. Whole-muscle LT RMS was calculated by averaging RMS across all 8 rows. Data were exported from OT BioLab+ (version 1.3.2, OT Biolettronica, Torino, Italy) as a .csv file in 0.1 second epochs. RMS for each contraction was defined as the maximum RMS value achieved over a 1.5 second interval within each arm elevation repetition. The data from the 1st and 10th repetition were removed and mean of RMS EMG values from 2nd through 9th repetitions was calculated for statistical analysis.

Statistical Analysis

Inferential statistical analysis was performed using SPSS (Version 25; IBM Corp, Armonk, New York, USA). A two-way repeated measures ANOVA was used to determine if differences in whole-muscle LT excitation existed between taping and loading

conditions. One-way repeated measures ANOVAs were also conducted to determine the effect of tape condition during the loaded condition on the spatial distribution of excitation for each row.

Normality for all procedures was assessed by Shapiro-Wilk's test of normality. Data were considered normally distributed if $p > .05$. Sphericity was assessed by Mauchly's test of sphericity. The assumption of sphericity was met if $p \leq .05$. For the two-way repeated measures ANOVA, outliers were considered to be studentized residuals greater than ± 3 standard deviations. For the one-way repeated measures ANOVAs, outliers were determined by boxplot inspection, with values greater than 1.5 box-lengths from the box considered outliers. Alpha was set at $p \leq .05$ for all statistical tests. A small effect size is considered $n^2 = 0.01$, a medium effect size is considered $n^2 = 0.06$, and a large is considered $n^2 = 0.14$ (Cohen 1988).

RESULTS

For comparison of whole-muscle LT excitation, analysis of studentized residuals indicated that the data were normally distributed, as assessed by Shapiro-Wilk's test of normality ($p > .05$). No outliers were present. One participant was removed from the analysis due to technical error. Another was removed due to incomplete data, resulting in $N = 20$ participants for the two-way ANOVA, and $N = 21$ for the one-way ANOVAs. Mauchly's test of sphericity was not met, $X^2(2) = 7.329, p = .026$. As such, a Greenhouse-Geisser correction was applied. There was no statistically significant interaction between tape and loading condition, $F(1.499, 28.476) = 1.368, p = .266$ (Figure 3). There was, however, a main effect for the loaded condition on whole-muscle LT excitation with a very large effect size, $F(1, 19) = 38.038, p < .001$, partial $\eta^2 = .667$. Across all tape conditions,

whole-muscle LT RMS in the loaded condition ($M = .055$ V, $SE = .005$) was significantly higher than the no-load condition ($M = .038$ V, $SE = .004$), with a mean difference of .017 V (95% CI, .011 to .023). There was no main effect of tape condition on whole-muscle LT RMS, $F(1.967, 37.38) = 0.370, p = .690$.

For comparison of spatial distribution of excitation, data for row one baseline, row five baseline, row five sham, and row six KT were not normally distributed as assessed by Shapiro-Wilk test of normality ($p < .05$). Mauchly's test of sphericity was not met $p < .05$ in row one in the loaded E-KT condition, as such, a Greenhouse-Geisser correction was applied. Row one contained four outliers (load; N-KT, E-KT and S-KT) and row eight contained three outliers (load; E-KT and S-KT) as assessed by boxplot inspection. Statistical analysis was conducted with and without the inclusion of outliers, and it was determined that the outliers did not affect the results. As such, outliers were not removed from analyses. There were no significant differences across tape conditions in grid row RMS (Table 1).

Achieved power for the whole muscle excitation load main effect was estimated post-hoc using G*Power (3.1.9.3, Faul, Erdfelder, Lang, & Buchner, 2007). Given an analyzed sample of $N = 20$, with $\alpha = 0.05$ and an effect size of 0.667 (partial η^2), the achieved power ($1 - \beta$ - error probability) is > 0.99 .

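### Experimental and sham tape were applied back to back with no wash-out, and the analysis does not address carry-over, so the E-KT minus S-KT contrast is open to a bias of unknown size and direction.

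*Combined protocol and SAP*

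**What the plan says.** The Design section of the combined protocol and SAP describes three taping conditions in one visit: none (N-KT), experimental (E-KT) and sham (S-KT).

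- Untaped condition: "A baseline trial (no KT; N-KT) was performed first".
- Tape order: "The order of the E-KT and S-KT conditions were randomized and counterbalanced". Numbers per sequence are not given.
- Load order was fixed, "with the no load condition preceding the loaded condition for each taping condition".
- Time under each tape: "Testing for each tape condition during both the no load and loaded conditions lasted approximately 10-minutes".
- Changeover: "No wash-out period was given between S-KT and E-KT taping conditions". As soon as one tape had been taken off after its task, the other went on.

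The Kinesio-tape section puts both tapes over the right upper trapezius. S-KT goes on without tension with the neck in neutral. E-KT goes on under tension with the muscle stretched.

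The Statistical Analysis section gives a two-way repeated-measures ANOVA (tape by load) for the whole muscle and one-way repeated-measures ANOVAs on tape for each grid row. Neither has a period or sequence term, and no first-period comparison is described. The Results section concludes "There was no main effect of tape condition on whole-muscle LT RMS" and finds no row differences, with no mention of carry-over.

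**The concern.** N-KT always came first and the unloaded task always preceded the loaded one. E-KT versus S-KT is therefore the only comparison protected by randomisation, and the only one with a sham control. E-KT versus N-KT cannot replace it, because it is confounded with time and test order.

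In the second taped period, the site had been taped and tested moments before. Counterbalancing averages out a simple period trend. It removes carry-over only if both tapes leave the same absolute residue, and the two are applied differently enough that this cannot be taken for granted. The documents give no evidence that an effect ends on removal, and no untaped reading was taken between the tapes that might show it.

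At stake is how far a finding of no difference can be read as showing that tape tension does nothing. If E-KT leaves more residue than S-KT in the direction of its effect, a real difference would be understated.

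**Working it through.** **Reported figures.** F(1.967, 37.38) = 0.370 gives p = .690, as stated. For load, partial η² = 38.038/(38.038 + 19) = 0.667, and the stated power above 0.99 reproduces (0.9999 or higher under the usual noncentrality conventions). That power concerns load. None is given for tape, and the text gives no E-KT minus S-KT estimate or interval.

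**Inputs.** From the documents: 22 participants, 20 analysed in the two-way ANOVA and 21 in the one-way ANOVAs; no wash-out; E-KT/S-KT order randomised. Assumed, because the documents do not give them: the persisting fraction c, the within-person correlation r, and equal sequences (10 and 10).

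**General bias.** Let τ be the true E-KT minus S-KT difference, p the period effect (second minus first taped period), and λE and λS what each tape leaves in the next period.

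- E-KT first: τ − p − λE
- S-KT first: τ + p + λS
- Mean of the two: τ + (λS − λE)/2
- S-KT-first minus E-KT-first: 2p + λE + λS

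The period effect cancels from the mean, but differential carry-over does not. The difference between sequences mixes period and carry-over effects, so it cannot diagnose either.

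**Common fraction c.** With tape effects e and s, λE = ce and λS = cs, so the mean is (e − s)(1 − c/2).

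**Different fractions.** Take e = 1 and s = 0.8, so the true difference is 0.20.

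- E-KT persists by 0.25 and S-KT by 0.5: bias (0.40 − 0.25)/2 = +0.075, estimate 0.275, an inflation of 37.5%.
- E-KT persists by 0.5 and S-KT by 0: bias (0 − 0.50)/2 = −0.25, estimate −0.05, a reversed sign.
- Equal absolute residues: bias 0.

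**Power and the omnibus test.** This illustration takes an inert sham (s = 0), N = 20 and a true effect of 0.66 SD of the paired difference, which has 80% power without carry-over. The condition means are then 0, e and ce/2, so the omnibus sum of squares is multiplied by 1 − c/2 + c²/4. Powers are simulated.

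| c | E-KT minus S-KT kept | Paired-test power | Omnibus sum of squares kept | Omnibus power |
|---|---|---|---|---|
| 0 | 100% | 80% | 100% | 84% |
| 0.25 | 87.5% | 69% | 89% | 80% |
| 0.5 | 75% | 55% | 81% | 75% |
| 1 | 50% | 25% | 75% | 69% |

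On the same squared scale, the E-KT minus S-KT contrast keeps 0.5² = 25% at c = 1, against 75% for the omnibus. In this case E-KT minus N-KT is not attenuated.

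**Unequal sequences.** With the same inert sham and a simple paired mean, if 8 to 12 of the 20 had E-KT first, the share kept at c = 1 runs from 1 − 8/20 = 60% to 1 − 12/20 = 40%.

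**Precision of the first taped period alone.** Adjusted for N-KT, its SE is proportional to √((1 − r²)·2/(n/2)), against √(2(1 − r)/n) for the crossover. The ratio is √(2(1 + r)): √3.6 = 1.90 at r = 0.8 and √3.8 = 1.95 at r = 0.9. As a simple change from N-KT the ratio is 2, and power for the 0.66 SD effect is about 29%.

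**The case against.** The absence of wash-out is openly stated, the order was randomised and counterbalanced, and nothing in the documents shows that any effect outlasts the tape. All of this is true. Carry-over here is a possibility that the design cannot exclude, not a demonstrated fault. Disclosing the gap does not, however, disclose what it means for the contrast, and the Results section gives no caveat.

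A reader might infer that any persisting tape effect must push the contrast towards zero, and by no more than half. The documents do not support that. Both statements need the two tapes to persist by the same fraction, between 0 and 1. With different fractions, the bias can vanish, inflate the difference or reverse its sign.

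A reader might also infer that carry-over accounts for the reported null. That does not follow either. The quoted test covers three conditions, and N-KT came before any tape, so nothing could carry over into it.

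It is also fair to say that the first-period comparison is weak, and that results by sequence cannot separate carry-over from fatigue or practice. Both points stand, and they limit what the re-analysis can show. They do not remove the reason for reporting the randomised contrast with its interval.

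**Conclusion.** The concern holds as a limit on the randomised contrast and on what may be concluded from it. E-KT minus S-KT may be biased by (λS − λE)/2, and neither size nor direction can be determined from the documents. The same exposure applies to the row-wise analyses.

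Attenuation of c/2 (12.5%, 25% and 50% at c = 0.25, 0.5 and 1) rests on additive effects, equal sequences and one common persisting fraction, so it illustrates the problem and is not a bound. The omnibus result (F = 0.370, p = .690) is less affected when the sham is inert, and carry-over is not shown to have produced it. The design choice is made and the data are in hand, so what remains is a reporting and sensitivity-analysis improvement that should be made.

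**What to change.** 1. Report the E-KT minus S-KT mean difference with its 95% CI from a model with a period term. Give numbers and estimates by sequence as description only. The period term guards against unequal sequence numbers; it does not remove carry-over.
2. Add the E-KT versus S-KT contrast from the first taped period, with each participant's N-KT value as covariate. Make it a fixed sensitivity analysis, reported whatever the other results show, and not a pre-test for carry-over. It is free of tape carry-over, but its SE is about 1.9 times the crossover SE for an assumed r of 0.8 to 0.9, so a non-significant result does not confirm absence of effect.
3. State in the conclusion that differential carry-over between the tapes cannot be excluded and may bias the contrast in either direction, with attenuation of c/2 if both effects persist by the same fraction c.
4. If further sessions are run, place an untaped interval, with an untaped reading, between the two tapes.

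Items 1 to 3 cost a short re-analysis of existing data and a sentence in the conclusion; the drawback is the imprecision of item 2. Item 4 lengthens a visit of about 45 minutes but needs no extra staff.

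### The blinding statement covers the no-tape condition, which cannot be blinded, so every comparison with no tape, including its share of the three-level tape F-test, is open and non-randomized

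*Combined protocol and SAP*

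**What the plan says.** The Kinesio-tape (KT) section of METHODS sets out the conditions, with the two tapes in a random sequence: "Each participant completed an arm elevation task under three taping conditions: first with no tape (N-KT), then with experimental-KT (E-KT) and sham-KT (S-KT) in random" […]. A little later in the same paragraph it gives the only statement on blinding in the document: "The therapists were the only individuals aware of the taping condition as the researchers and participants were blinded". Nothing in that sentence limits it to the two tapes.

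The Design section confirms the order: "A baseline trial (no KT; N-KT) was performed first, followed by both an experimental-KT (E-KT) and sham-KT (S-KT) condition". Only the order of E-KT and S-KT is randomized and counterbalanced.

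The Kinesio-tape section also describes how each tape goes on. For S-KT there is no stretch, and "the participant was instructed to look straight ahead to maintain a neutral neck and shoulder position". For E-KT, "the UT was placed in a stretched position by instructing the participant to bring their chin to chest and rotate to their left shoulder", and the tape is laid down at about 125% after being stretched further and eased back.

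The Statistical Analysis section tests tape as a factor in a two-way repeated measures ANOVA on whole-muscle lower trapezius (LT) amplitude, and in one-way ANOVAs for each grid row under load. It names no pairwise tape contrast. RESULTS gives the whole-muscle tape effect as F(1.967, 37.38) = 0.370, p = .690.

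**The concern.** Read as written, the sentence tells the reader that neither participants nor researchers knew which of the three conditions was being tested. That cannot be so for N-KT.

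The outcome is recorded by an instrument, which removes subjective scoring. It does not remove the participant from the measurement. The signal comes from a voluntary arm raise in which participants keep to a metronome and copy a research assistant, and the value kept is a maximum over a short window in each repetition. Effort and speed can move it. Someone who knows that no tape is on, or that tape has just been put on, may move differently.

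What is at stake is attribution. A difference from N-KT, or the lack of one, mixes the effect of tape with expectation, with performance, and with always going first. The sham condition exists to separate these, but the whole-muscle tape test pools the sham comparison with the open ones.

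**Working it through.** No sample-size or error-rate figure is involved, so most of the check sets the statements side by side.

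**1. Which comparisons can be blind.** Three conditions give C(3,2) = 3 pairs.

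| Pair | Order randomized? | Condition hidden? |
|---|---|---|
| N-KT vs E-KT | No, N-KT always first | No, N-KT is untaped |
| N-KT vs S-KT | No, N-KT always first | No, N-KT is untaped |
| E-KT vs S-KT | Yes, counterbalanced | Claimed; at risk from posture and tension |

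Two of the three are open, because of N-KT alone. Head posture plays no part in that count, since it differs only between the two tapes.

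**2. What the posture difference shows.** Each participant received both tapes, the second straight after the first came off, so the two applications could be compared directly. One involves a flexed, rotated neck and stretched tape; the other involves neither. A participant would probably notice. Noticing a difference is not the same as knowing which tape is the sham. The consent text says "Participants received complete written and verbal details of the experimental procedures and potential risks involved prior to providing informed consent", but not whether those details disclosed a sham. Nor do the documents say whether researchers watched the taping, whether the tape was covered, or whether blinding was checked.

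**3. Where N-KT enters the analysis.** First, the reported figure: the upper tail of F = 0.370 on (1.967, 37.38) degrees of freedom is 0.690, as stated. Partial eta squared is 0.370 × 1.967 / (0.370 × 1.967 + 37.38) = 0.728 / 38.108 = 0.019. Before the Greenhouse-Geisser correction, a three-level factor has 2 degrees of freedom. One can be assigned to E-KT vs S-KT (randomized, sham-controlled). The other is then N-KT against the mean of the two tapes (open, fixed order). The single F averages over both and does not report either.

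**4. What separating them could change.** The two parts together amount to 2 × 0.370 = 0.740 in units of the pooled error. The Greenhouse-Geisser factor is 1.967 / 2 = 0.9835. With two error components in the ratio (1 + d) : (1 − d), this factor equals 1 / (1 + d²), so d = √(1/0.9835 − 1) = 0.130, and no contrast's own error is below 0.870 of the pooled error. For E-KT vs S-KT averaged over the two loads, F(1, 19) is therefore at most 0.740 / 0.870 = 0.85, p about .37 or higher. A paired test on the same 20 participants would not become significant. Its estimate, direction and confidence interval cannot be recovered from the reported F.

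**The case against.** The strongest reply is that context limits the sentence. It directly follows the statement about who applied the tape, and the Design section calls N-KT a baseline trial ("A baseline trial (no KT; N-KT) was performed first"), so what the therapists alone knew is which tape went on. That is probably what was meant. It does not rescue the wording, because the paragraph has just defined no tape as a taping condition. It does make the repair mainly one of wording.

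The task is also standardized: metronome pace, a demonstrator, full abduction, fixed load, familiarization, and first and last repetitions dropped. This reduces the room for performance effects. It does not remove them or make N-KT blind.

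Further, there is no positive tape finding for expectation to explain, and the plan names no pairwise contrast. Both are true. Open performance effects can hide a difference as well as create one, though the documents give no evidence that they did.

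Three stronger readings are tempting and should be resisted:

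- A reader might infer that the posture difference broke the blind between E-KT and S-KT. The documents show a risk only.
- A reader might infer that the ANOVA was presented as a blinded comparison. Blinding is mentioned only in the Kinesio-tape section; neither the analysis text nor the results describe the test that way.
- A reader might infer that EMG extraction was biased because condition codes are not said to be hidden. The Data processing section gives a defined maximum-RMS rule, and no fault is shown.

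**Conclusion.** The blinding statement is too broad. Comparisons with N-KT, two of the three pairs and part of the three-level tape test, are open and non-randomized. Only E-KT vs S-KT is both randomized and capable of being masked, and how well it was masked is undocumented.

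This rests on reading the term taping condition as the paragraph itself defines it, and on the practical point that bare skin in a known first trial cannot be concealed. It does not depend on any view of how far knowledge of the condition shifts EMG amplitude; that size and its direction cannot be derived from the documents.

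The null tape result is not overturned. On the reported figures the load-averaged sham contrast would also be non-significant. What changes is which comparison can carry the conclusion about tape, and how precisely it does so. The point is worth correcting, mainly as reporting and interpretation.

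**What to change.** - In the Kinesio-tape section, state that N-KT was unblinded, and limit the blinding claim to which of E-KT or S-KT was applied.
- Have the sponsor describe what participants and researchers were told and could see, including whether a sham was disclosed, whether researchers were present at taping, and whether blinding was checked. The revised text should not say that participants were unaware of which tape was the sham unless the sponsor can confirm it.
- List the difference in head posture and tape tension at application as a limitation on masking.
- Report the paired E-KT minus S-KT difference in whole-muscle LT RMS with its 95% confidence interval as the contrast supporting the tape conclusion.
- Label any comparison with N-KT as an open before-after comparison. Keep the three-level F-test as reported.

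**Cost.** A few sentences and one added contrast from data already collected; no new participants or measurements. The blinding claim becomes less favourable. Because results are already reported, the contrast must be labelled as added after the fact.

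### Does the mismatch between three beats at 40 beats per minute and a repetition of about 3 seconds leave the outcome undefined?

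*Combined protocol and SAP*

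**What the plan says.** Under METHODS, Repeated arm elevation task, the tempo is given as follows: "A research assistant performed the arm elevation task at a rate of 40 beats per minute while participants were asked to follow a metronome". The next sentence gives the length of one cycle: "Each repetition lasted for a total of three beats, or ~3 seconds, beginning with their arms by their sides". The beats are then tied to events in the movement. On the way up and back, "the first beat occurred at maximal abduction, followed by descending back to starting position where the second beat occurred". After that, "The third beat acted as a rest beat before beginning the next repetition and continued this for a total of 10 repetitions". The movement runs from arms at the side to 180 degrees of abduction. The same task description applies to every combination of tape and load.

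Under Data processing and extraction, the outcome is described thus: "RMS for each contraction was defined as the maximum RMS value achieved over a 1.5 second interval within each arm elevation repetition". Data were exported in epochs of 0.1 s, and the values from repetitions 2 to 9 were averaged for analysis. The section does not say when the 1.5 s interval starts or which phase of the movement it covers.

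**The concern.** The rate, the beat count and the duration cannot all be right. Three beats at 40 per minute do not fit into 3 s, and an approximation sign does not cover a 50% gap. The text counts the rest beat among the three, so the duration cannot be read, as written, as moving time alone.

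The stakes seem higher because the outcome is taken from an interval of fixed length inside each repetition. If the length of the repetition is in doubt, so apparently are the speed of the arm and the share of the movement that the interval spans. Speed of movement can be expected to affect EMG amplitude (general reasoning; the document does not say so). A reader might conclude that the outcome cannot be interpreted until the tempo is recovered from the recordings and the RMS values are extracted again.

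**Working it through.** **Inputs.** From Repeated arm elevation task: 40 beats per minute; three beats per repetition (one up, one down, one rest); stated duration about 3 s; range 0 to 180 degrees; 10 repetitions. From Data processing and extraction: a 1.5 s interval and 0.1 s epochs.

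**Attempt to reproduce the stated duration.** Duration = beats x 60 / (beats per minute).

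- Literal reading: 3 x 60/40 = 4.5 s. The stated 3 s is not reproduced; the excess is (4.5 - 3)/3 = 50%.
- Two beat intervals, meaning ascent plus descent, or equally first beat to third beat: 2 x 60/40 = 3.0 s. This gives the stated figure exactly, but leaves out one of the three beats that the sentence counts.
- Three beats in 3 s: this needs 3/3 x 60 = 60 beats per minute, a rate that the document does not contain.

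**What each tempo would imply.**

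| Quantity | 40 beats/min (stated) | 60 beats/min (back-calculated) |
|---|---|---|
| Beat length | 1.5 s | 1.0 s |
| Full cycle | 4.5 s | 3.0 s |
| Moving time | 3.0 s | 2.0 s |
| Mean ascent speed | 180/1.5 = 120 degrees/s | 180/1.0 = 180 degrees/s |
| Ten repetitions | 45 s | 30 s |
| 1.5 s as share of cycle | 1.5/4.5 = 33% | 1.5/3.0 = 50% |
| 1.5 s as share of moving time | 1.5/3.0 = 50% | 1.5/2.0 = 75% |

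**Which column the text supports.** Two details favour the first. Moving time at the stated rate equals the stated 3 s. The outcome interval of 1.5 s equals exactly one beat at that rate, whereas at 60 beats per minute it would be one and a half beats and match no phase. The likeliest account is that 3 s is the moving time, attached by mistake to the full cycle.

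**Does tempo fix what the interval measures?** No. An interval of 1.5 s at 40 beats per minute has the same length as the ascent, but it coincides with the ascent only if it starts at movement onset, and the document does not say that it does. Started half a beat later, it would straddle the top of the movement at the same tempo. The wording also allows another reading: a 1.5 s search interval (1.5/0.1 = 15 epochs) from which the highest epoch is taken. On that reading the share of the cycle covered does not define the outcome. In every case the missing information is the start point, which correcting the duration does not supply.

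**Effect on the comparisons.** The two-way repeated measures ANOVA (tape by load) and the one-way ANOVAs by row (tape, loaded condition only) compare each participant with themselves. One metronome rate is described for all conditions. If every condition ran at the same tempo, whichever it was, tempo is common to both sides of each contrast and the discrepancy gives no reason to expect bias. No printed duration enters any RMS value, F statistic or confidence interval, so changing 3 s to 4.5 s in the text leaves every result as it stands.

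**The case for a change.** The best case for action is that the benign reading is an inference. The sentence says three beats in total, and the rest beat is one of them, so at least one printed figure is wrong on any reading. A laboratory repeating the study could move at 120 or at 180 degrees/s and claim to follow part of the text. If the cycle really lasted 3 s, a 1.5 s interval could not lie inside a single 1.0 s phase and would have to cross the top of the movement or take in rest. A check would also seem cheap: if the recordings were kept, the spacing of the EMG bursts should separate cycles of 4.5 s from cycles of 3 s, and 0.1 s epochs are fine enough to show it.

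Part of this stands. The sentence is wrong as printed, and exact replication would be helped by giving moving time and full cycle separately, after a look at the recordings.

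The rest does not carry. The faster tempo rests on a single figure that the authors marked as approximate, against an explicit rate. The doubt about phase exists at 40 beats per minute too, so it cannot be charged to the arithmetic. Re-extraction with an interval locked to a phase supposes a misalignment that nobody has shown. It also needs a marker of arm position, and the document describes no goniometer, motion capture or event marker, so phase might not be recoverable from EMG alone.

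**Conclusion.** The inconsistency is confirmed: 4.5 s by the stated rate and beat count against about 3 s printed. It is a clerical slip in describing the task, with a probable explanation (moving time reported as cycle time), and it bears on exact replication only. Its effect on the reported tape and load comparisons is nil, and no change to the outcome definition or the analysis follows from it.

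This rests on two assumptions: the metronome ran at the one stated rate in every condition, as the document describes, and participants kept to it about equally well with and without load and tape. The mismatch in the printed duration gives no ground to doubt either. The unstated start of the 1.5 s interval is a separate gap in reporting, to be judged on its own merits.
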